**Abstract**

Alveolar bone remodeling after tooth extraction may result in significant ridge resorption and inadequate bone volume for implant placement. Several methods have been designed for ridge augmentation, among which is the new technique of osseodensification, using the Densah® burs by Versah® (Versah®, LLC, Jackson, MI, USA). This method compresses the trabecular bone to periphery of the osteotomy site and has shown up to 80% ridge expansion in animal histological studiesi,ii,iii,iv,v,vi. Apart from being an animal model with a short follow-up, another limitation of these studies is the lack of three-dimensional evaluation of the change in morphology of the ridge. Human clinical studiesvii,viii,ix,x,xi have reported similar results, but they do not evaluate if this bone volume is retained during osseointegration and loading periods. No standardization method or long-term evaluation of peri-implant health was reported.

Although promising improvements in bone density and volume have been reported, there is a lack of clinical evidence in humans with adequate follow-up period. Our research is motivated by this gap and our objective is to further investigate this phenomenon. We propose a human case series to evaluate the implant survival and success rates when using the osseodensification technique for osteotomy preparation.

Approximately 40 implants from patients seeking treatment at the University of Oklahoma, College of Dentistry will be recruited for this study. Osteotomies will be prepared using the osseodensification technique and implants will be placed immediately after. The implants will be from a single manufacturer (Roxolid® SLA® Bone Level Tapered; Straumann®, Institut Straumann AG, Basel, Switzerland). Volumetric analysis of alveolar ridge will be studied using intra-surgical direct measurements and CBCT imaging. A custom stent will be fabricated to standardize the clinical and radiographic measurements. The stent will have positions for a Weiss modified curved bone caliper (Hu-Friedy®, Chicago, IL, USA) to be inserted at buccal and lingual and measure ridge width at, at 2mm and 4, 3, 4 mm apical to edentulous alveolar ridge. These holes will be filled with gutta-percha and CBCTs will be taken with this stent in place, to standardize the measurements on CBCT. Changes in peri-implant bone density will be analyzed on standardized ~~periapical and~~ bitewing radiographs, using the ImageJ software (National Institute of Health, Bethesda, Maryland, USA). Implant stability quotient (ISQ) values will be recorded with a resonance frequency analysis system (Osstell®, Gothenburg, Sweden).

Calibrated examiners will assess implant survival and biological or restorative complications and failures. Sites will be evaluated throughout osseointegration and one year after final restoration is delivered.

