## 1. **Specific Aims**

Primary Aim:

Evaluate the efficacy of osseodensification technique in regards to increase in alveolar bone volume and density at time of implant placement and retention of this volume throughout osseointegration and loading.

Secondary Aim:

Evaluate the osseodensification technique for preparation of implant osteotomy, in regards to implant stability, survival and failure rate, probing pocket depth, plaque index, bleeding index, gingival index, interproximal crestal bone level changes, biological complications (i.e. peri-implant mucositis, peri-implantitis), and restorative complications (i.e. screw loosening, porcelain fracture). These outcomes will be evaluated from the time of implant placement until 1 year after final restoration is delivered.

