In a studyError! Bookmark not defined. on porcine oral alveolar bone, 80% ridge expansion was recorded immediately after osseodensification. After 4 weeks of healing, the animals were euthanized and samples were processed for histological evaluation. This was the first study to evaluate the amount of ridge expansion in atrophic mandibular ridge. Apart from being an animal model with a short follow-up, another limitation of this study is the method of recording the expansion. Transverse dimension of the ridge was measured with a periodontal probe, immediately before and after osseodensification. Measurements were only at one dimension, without three-dimensional evaluation of the change in morphology of the ridge. Also, there is no record if this bone volume is retained during osseointegration and loading.

A few human case reportsvii,viii,ix and case seriesx,xi have reported significant ridge expansion immediately before and after osseodensification. They evaluated the expansion by measuring the ridge width at a crestal and an apical point, which again lacks an evaluation of ridge morphology in a three-dimensional view. Using the same methodology, a recent retrospective studyxi on 28 implants found a mean expansion of  $1.8 \pm 1.1$  mm at the crest and  $0.9 \pm 0.8$  mm at 10 mm mark apical to the crest, immediately after expansion. They reported greater expansion at narrow ridges. None of the mentioned studies report on retention of this volume over time, nor was standardization methods or evaluation of peri-implant health reported.

Although promising improvements in bone density and volume have been reported, there is a lack of clinical trial in humans with adequate follow-up period. Our research is motivated by this gap and our objective is to further investigate this phenomenon. We propose a human case series to evaluate the amount of ridge expansion and the survival and success rates of implants placed by using the osseodensification technique.

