### 3. **Research Design and Methods**

This case series will assess the efficacy for alveolar ridge expansion and change in peri-implant density when prepared by the osseodensification technique. The retention of this volume throughout osseointegration and loading will be evaluated. The changes in bone volume will be recorded by CBCT and intra-surgical direct measurements. A standardizing stent will be used to for direct measurements with a caliper. Radiopaque markers on this stent will guide the measurements on the CBCT. CBCT will be taken before and after osseodensification, and 1 year after delivery of final restoration. Standardized ~~periapical and~~ **bitewing** radiographs will be taken as well to evaluate marginal bone loss and peri-implant bone density. Calibrated examiners will evaluate implant survival and failure rate, ISQ value,

peri-implant pocket depth, plaque index, bleeding index, gingival index, biological and restorative complications.

All the surgical interventions and follow-up appointments will be conducted at the University of Oklahoma, Graduate Periodontics clinic. Restorative interventions will be scheduled with the restorative dentist of the patient's choosing. Approximately 10 visits are anticipated for each patient. Additional appointments may be needed depending on surgical or restorative complications that need attention or intervention. Following the completion of the study, the participants are placed on appropriate recall schedule either at the Graduate Periodontics clinic or referred to their dentist of choosing.

Informed consent will be obtained from the patients. Appropriate steps will be taken to protect collected data and de-identify it before data analysis. Identifiers will be removed and the de-identified information may be used for future research without additional informed consent from the subjects. Patient information will be protected according to the privacy regulations of the federal Health Insurance Portability and Accountability Act of 1996 (HIPAA).

*\* Research specific procedure*

Planned Visits:

1. Pre-screening
  - a. Preliminary review of eligibility criteria\*
2. Screening
  - a. Confirm eligibility\*
  - a.b. Informed consent\*
  - c. Diagnostic casts
3. Fabrication of measurement stents
  - a. Fabrication of custom stent for measurement of alveolar ridge width\*

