#### 7.8. 3-4-month follow-up after implant placement

- a. Evaluate wound closure, epithelialization, and any complications
- b. Evaluate pocket depth, plaque index, bleeding index, and gingival index
- c. Measure ISQ by using Osstell Beacon (Osstell®, Gothenburg, Sweden)
- d. Take standardized ~~periapical and~~ bitewing and non-standardized periapical

- radiographs
- e. Perform localized prophylaxis
- f. Take intraoral photos
- g. Uncover the implant, if needed (and 2-week follow-up after uncovering)
- ~~8.9.~~ Restoration by the restorative dentist
- ~~9.10.~~ 2-week follow-up after implant restoration
  - a. Evaluate pocket depth, plaque index, bleeding index, and gingival index
  - b. Evaluate biological (i.e. peri-implant mucositis, peri-implantitis) and restorative complications (i.e. screw loosening, porcelain fracture)
  - c. Take standardized ~~periapical and~~ bitewing and non-standardized periapical radiographs
  - d. Perform localized prophylaxis
  - e. Take intraoral photos
- ~~10.11.~~ 1-year Follow-up after implant restoration
  - a. Evaluate pocket depth, plaque index, bleeding index, and gingival index
  - b. Evaluate biological (i.e. peri-implant mucositis, peri-implantitis) and restorative complications (i.e. screw loosening, porcelain fracture)
  - c. Take standardized bitewing and non-standardized periapical radiographs
  - ~~e. Take standardized periapical and bitewing radiographs~~
  - d. Take standardized CBCT, limited to the implant site\*
  - e. Perform localized prophylaxis
  - f. Take intraoral photos
- ~~11.12.~~ Data analysis
  - a. Evaluation of change in peri-implant bone density, using the ImageJ software (National Institute of Health, Bethesda, Maryland, USA)\*
  - b. Statistical analysis of changes in the parameters throughout the study period\*

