## 8. Statistical Methods

The biostatistics department at OUHSC will be utilized to review the data and perform statistical evaluation. Mean values, standard deviations, and medians will be calculated for clinical measurements. We will compare the bone volumetric changes before ridge expansion to different time points throughout healing. In addition, we will determine the implant survival and success rates by evaluating the probing pocket depth, bleeding index, gingival index, interproximal crestal bone level changes, biological and restorative complications of implants placed by the osseodensification technique. A fixed-effects regression model can account for correlations between repeated measures taken at each implant over time. This model can estimate a regression equation that describes the within-group changes.

Approximately 40 implants from patients seeking treatment at the University of Oklahoma, College of Dentistry will be recruited for this study. It is estimated that this sample size will provide 90% power of the test.

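### No masking of time point, image coding or reading order is specified for CBCT ridge width or ImageJ density, so a reading shift could hide bone loss in the retention result

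*Combined protocol and SAP*

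**What the plan says.** Section 1 makes the gain in bone volume and density at placement, and the "retention of this volume throughout osseointegration and loading", the primary aim. Section 3 describes a case series with no comparison group. On imaging it says "CBCT will be taken before and after osseodensification, and 1 year after delivery of final restoration"; the list of planned visits puts the middle scan at the 2-week visit. Section 8 compares later time points with the state before expansion.

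On who assesses what, the Abstract says "Calibrated examiners will assess implant survival and biological or restorative complications and failures". Section 3 adds stability readings, pocket depth and the clinical indices, and Section 2 adds crestal bone level on bitewings. None of these lists includes CBCT width or ImageJ density. For density, the data analysis step at the end of the planned visits says only "Evaluation of change in peri-implant bone density, using the ImageJ software". It names no reader and no reading order.

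The plan has four relevant safeguards:
- Gutta-percha markers in a stent worn at each CBCT fix the levels at which width is measured, 2 and 4 mm apical to the ridge.
- A custom bite registration standardizes the bitewings.
- Caliper readings at surgery give a second measure of the initial gain.
- Identifiers are removed: "Appropriate steps will be taken to protect collected data and de-identify it before data analysis".

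**The concern.** The safeguards control how images are acquired, the level at which width is read, and privacy. None controls where the reader places the bone edge or draws the density region, and none hides which visit is being read.

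In a single-arm study each conclusion is a before-after difference. A reading shift tied to the visit therefore goes straight into the result, with no concurrent group to cancel it. Retention is most exposed, because the study sets out to fill a gap in evidence on exactly that question. A reader who expects the expanded bone to be kept could place the 1-year edge nearer to the 2-week one and so understate loss. If only unmasked readings exist at the end, no analysis can repair this.

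**Working it through.** **The plan's own figure.** Section 8 states "Approximately 40 implants from patients seeking treatment at the University of Oklahoma, College of Dentistry will be recruited for this study" and "It is estimated that this sample size will provide 90% power of the test". It names no test, alpha, effect or SD. At an assumed two-sided 5%, 40 implants give 90% power for a standardized paired change of (1.960 + 1.282)/√40 = 0.51 (normal approximation) or 0.53 (noncentral t).

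The only effect sizes in the documents come from the retrospective study cited in Section 2: 1.8 (SD 1.1) mm at the crest, and 0.9 (SD 0.8) "mm at 10 mm mark apical to the crest, immediately after expansion". Their ratios are 1.8/1.1 = 1.64 and 0.9/0.8 = 1.13. Either gives power above 99.9% at n = 40, and 90% would need 7 and 11 implants respectively (two-sided t). So the 90% cannot be reproduced from the documents. It is uncheckable, which does not show that it is wrong.

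**Inputs for the illustration, all assumed.**
- n = 40 independent implants with no dropout. The number of patients is not stated.
- Paired t-test of 1-year minus 2-week width, two-sided 5%, df 39, critical value 2.02.
- SD of change 0.8 or 1.1 mm, borrowed from immediate expansion in the cited study because no SD of later change is given.
- True mean loss L = 0.5 mm. With 90% power the detectable loss would be 0.526 × 0.8 = 0.42 mm or 0.526 × 1.1 = 0.58 mm, so 0.5 mm lies in that range.
- Hidden part b = 0.1 to 0.3 mm, constant across implants, SD unchanged.

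**Formula.** SE = SD/√40, noncentrality = (L − b)/SE, and power from the noncentral t.

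| SD (mm) | SE (mm) | b (mm) | (L − b)/SE | Power |
|---|---|---|---|---|
| 0.8 | 0.126 | 0 | 3.95 | 97% |
| 0.8 | 0.126 | 0.1 | 3.16 | 87% |
| 0.8 | 0.126 | 0.2 | 2.37 | 64% |
| 0.8 | 0.126 | 0.3 | 1.58 | 34% |
| 1.1 | 0.174 | 0 | 2.87 | 80% |
| 1.1 | 0.174 | 0.1 | 2.30 | 61% |
| 1.1 | 0.174 | 0.2 | 1.72 | 39% |
| 1.1 | 0.174 | 0.3 | 1.15 | 20% |

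With an SD of 0.5 mm the same 0.5 mm loss is found almost always without a shift, in 96% of studies with b = 0.2 mm and in 69% with b = 0.3 mm.

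**Effect on the estimate.** With b = 0.2 mm the expected estimate of loss is 0.5 − 0.2 = 0.3 mm, an understatement of 0.2/0.5 = 40%. If each change were instead shrunk by the same proportion, mean and SD would fall together. Power would then hold, but the estimate would be just as wrong.

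The documents give no numerical basis for a similar calculation on density.

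**The case against.** The strongest reply is that the plan is silent and has not chosen unmasked reading. A reader might infer that the examiners know the time point, or that the same calibrated examiners read every image. Neither is in the documents: the calibrated-examiner sentences cover survival, complications, clinical measures and crestal bone level. What can be said is that no masking is specified and no reader is named for the two image outcomes of the primary aim.

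A reader might also infer that a reading shift creates false findings of change. With a true change of zero, a constant shift of 0.1, 0.2 or 0.3 mm would raise the 5% error rate to 9%, 20% or 39% at SD 1.1 mm. That arithmetic is sound, but it answers a different question. If there is no true change, pulling the 1-year reading towards the 2-week one creates no shift. The harm from an expectation of retention is missed loss.

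The inputs are open to challenge. The size and direction of any shift are unknown. The SDs describe immediate expansion, and the 0.8 mm figure comes from 10 mm apical, whereas this plan measures at 2 and 4 mm. Several implants in one patient would usually widen the intervals. All of this stands, so the figures show sensitivity and are not a forecast.

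Masking would also be incomplete. Pre-surgical images show no implant, so the comparison with the state before expansion, which is the one Section 8 names, keeps one identifiable side. Caliper readings are made at surgery. Healing signs, or xenograft where it was placed, may reveal the visit. Cropping could also remove bone needed for crestal level on the same bitewings. These points limit the remedy but do not remove its value for 2-week against 1-year, the contrast that bears most directly on retention.

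**Conclusion.** The gap is real and worth closing, within limits. The plan specifies no masking of time point, image coding or reading order for CBCT width or ImageJ density, and it does not say who reads them. In this design a shift of a few tenths of a millimetre would matter: hiding 0.2 mm of an assumed 0.5 mm loss takes power from 97% to 64%, or from 80% to 39%, for SDs of 0.8 and 1.1 mm. This rests on 40 independent implants, a constant shift and borrowed SDs. The documents do not show that biased reading will occur, and masking would not protect the initial gain.

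A better method is within reach. The CBCTs are stored images, both post-placement scans show the implant, and ImageJ work is already listed after the 1-year visit.

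**What to change.** Add to the data analysis step:

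- Name who reads CBCT width and ImageJ density, using the study's existing readers.
- Prepare coded post-placement CBCT slices, and copies of the post-placement bitewings for the density reading, with dates removed and the restoration cropped out. Crop all of them in the same way, so that the crop itself does not reveal the visit. Keep the stent markers and measurement levels in view.
- Keep uncropped bitewings for crestal bone level.
- Read all coded images in one random sequence after the last visit. Study personnel who do not read hold the key, which stays closed until the readings are locked.
- Re-read a subset and report repeatability, which would supply the reader error now missing.
- State that the pre- versus post-placement contrast and the caliper readings are unmasked.

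The cost is some file preparation, a key holder from existing personnel, and a later reading date. No extra scan, visit or image reader is needed. Masking will be imperfect where healing signs or graft remain visible.

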## 1. **Specific Aims**

Primary Aim:

Evaluate the efficacy of osseodensification technique in regards to increase in alveolar bone volume and density at time of implant placement and retention of this volume throughout osseointegration and loading.

Secondary Aim:

Evaluate the osseodensification technique for preparation of implant osteotomy, in regards to implant stability, survival and failure rate, probing pocket depth, plaque index, bleeding index, gingival index, interproximal crestal bone level changes, biological complications (i.e. peri-implant mucositis, peri-implantitis), and restorative complications (i.e. screw loosening, porcelain fracture). These outcomes will be evaluated from the time of implant placement until 1 year after final restoration is delivered.

## 2. **Background and Significance**

Alveolar bone remodeling after tooth extraction may result in up to 50% ridge resorption within the first 3 monthsxii. This remodeling may result in inadequate bone volume for implant placement. Several methods have been designed for ridge augmentation, among which are guided bone regeneration, ridge splitting, and osteotome expansion technique. Recently the new technique of osseodensification has been proposed, by the use of non-subtracting drills, to compress the trabecular bone to periphery of the osteotomy site rather than removing itxiii. This simple method will expand the alveolar ridge without the additional need for bone augmentation.

Densah® burs by Versah® use the osseodensification technique to compact and auto-graft the osteotomy. These drills are designed with more than 4 lands for more precise movement and less potential chatter. The clockwise rotation can cut the bone and the counterclockwise direction will densify the bone. The cutting mode can be used in hard, trabecular bone. It is recommended by the manufacturer to avoid densifying xenografts, prepare the osteotomy 1.0 mm deeper than the final implant length, and to use this technique in areas with  $\geq 2$ mm of trabecular bone and  $\geq 1/1$  trabecular/cortical bone ratio. Therefore, the ideal minimum ridge to expand is 4mm (2mm trabecular core + 1mm cortex on each side)xiv.

Histological studies on sheepi,ii,iii and porcineiv,v,vi have shown an increase in primary stability, bone mineral density, and percentage of bone-to-implant contact with the osseodensification technique, when compared to conventional drilling. Although promising results were recorded by the above-mentioned studies, they present with multiple limitations as well. In the two studies on porcine modeliv,v, the osteotomies were performed on extracted tibial bone, which did not allow evaluation of healing over time. The osteotomies on sheep modelsi,ii,iii were either on ilium or vertebral body, with up to a 2-month follow-up. The extraoral animal model cannot be directly translated to human oral cavity and the short follow-up does not fully evaluate implant success. Furthermore, these studies did not

evaluate the effect of osseodensification on implant survival and success when loaded with restoration.

In a studyError! Bookmark not defined. on porcine oral alveolar bone, 80% ridge expansion was recorded immediately after osseodensification. After 4 weeks of healing, the animals were euthanized and samples were processed for histological evaluation. This was the first study to evaluate the amount of ridge expansion in atrophic mandibular ridge. Apart from being an animal model with a short follow-up, another limitation of this study is the method of recording the expansion. Transverse dimension of the ridge was measured with a periodontal probe, immediately before and after osseodensification. Measurements were only at one dimension, without three-dimensional evaluation of the change in morphology of the ridge. Also, there is no record if this bone volume is retained during osseointegration and loading.

A few human case reportsvii,viii,ix and case seriesx,xi have reported significant ridge expansion immediately before and after osseodensification. They evaluated the expansion by measuring the ridge width at a crestal and an apical point, which again lacks an evaluation of ridge morphology in a three-dimensional view. Using the same methodology, a recent retrospective studyxi on 28 implants found a mean expansion of  $1.8 \pm 1.1$  mm at the crest and  $0.9 \pm 0.8$  mm at 10 mm mark apical to the crest, immediately after expansion. They reported greater expansion at narrow ridges. None of the mentioned studies report on retention of this volume over time, nor was standardization methods or evaluation of peri-implant health reported.

Although promising improvements in bone density and volume have been reported, there is a lack of clinical trial in humans with adequate follow-up period. Our research is motivated by this gap and our objective is to further investigate this phenomenon. We propose a human case series to evaluate the amount of ridge expansion and the survival and success rates of implants placed by using the osseodensification technique.

Calibrated examiners will evaluate implant survival rate, peri-implant pocket depth, plaque index, bleeding index, gingival index, interproximal crestal bone level changes on standardized ~~periapical~~ **bitewing** radiographs, biological and restorative complications. Volumetric analysis of alveolar ridge will be studied using cone-beam CT imaging and intra-surgical direct measurements. These outcomes will be evaluated from the time of implant placement until 1 year after final restoration is delivered.

